In measuring any parameter of health, it needs to be noted that measurements need to be evaluated in reference to other measures in the body. An elevation of one parameter may seem to be an issue as it is out of range and yet when viewed holistically, the data can be normal for the age and gender. The data will all be viewed accordingly and any values that are of concern will be put into context both in the analysis and in communication with the subject and local physician. This is especially important when one considers that in general there is a background level of most metals and trace elements in everybody. The levels of CoCs found in the community of Port Colborne will be compared to standard reference ranges. In the analysis, the confounder data collected will be utilized to add context to the data. There may be instances where the very nature of the confounder will result in the fact that an outcome could be due to more than one cause. Confounders include, diet and food in general. Arsenic levels can be elevated by the ingestion of shellfish. This can be differentiated by utilizing a fractionated arsenic measure methodology that will identify organic and non-organic arsenic. The asthma symptoms and signs could be due to atopy (genetic susceptibility to allergies) in the subject, and therefore the person has hyperreactive airways to a number of airborne irritants. Hypersensitivity to nickel could be confounded by the level of jewelry that pierces the skin. Cobalt could be elevated due to the presence of a prosthesis device. This will all be clearly addressed during the review of each participants data and in the analysis. Other confounders that will be taken into account are lifestyle factors, such as smoking or use of alcohol. These are associated with many health risks including cancer and heart disease, use of prescription medications, OTC, Health supplements, such as those that contain vitamin B12 and other natural products. The use of medicinal products,

although treating one set of specific symptoms, may effect other haematological parameters. For example the use of Lithium can increase TSH levels, certain anti-inflammatory drugs can effect T-4 levels, codeine can effect liver enzyme levels.

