Comparison of the Mean Levels of Selected Biological Measures, by Sampling Areas,
CHAP Comprehensive Health Questionnaire, Fall 2002

	Area 3	Areas 1, 2, 4, 5	Total for Port Colborne	p-value [†]
	Mean (s.d)*	Mean (s.d)	Mean (s.d)*	
Haemoglobin				
White Blood Cell Count				
Red Blood Cell Count				
Haematocrit				
Mean Cell Volume of Red Cells				
Mean Hemoglobin Concentration of Red Cells				
Platelet Count				
Red Cell Distribution Width				
Mean Platelet Volume				
Differential Leukocyte Count				
Bilirubin				
Creatinine				
Plasma Cotinine				
Plasma Screen for Concentration of TSH				
Blood Urea Nitrogen				

[†] p-value is based on an ANOVA for comparing the means between Area 3, and Areas 1, 2, 4, and 5; after adjusting for difference in the age and sex distribution of the two populations.

* s.d. = standard deviation

Table 8.
Comparison of the Non-Specimen Tests Among Participants, by Sampling Areas,
CHAP Comprehensive Health Questionnaire, Fall 2002

	Area 3	Areas 1, 2, 4, 5	Total for Port Colborne	p-value [†]
	Mean (s.d) [*]	Mean (s.d)	Mean (s.d.)	
Calculated BMI				
Electrocardiogram	---	---	---	---
Blood Pressure				
Carbon Monoxide Breath Test				
Forced Expiratory Volume in 1 second				
Forced Vital Capacity				
Peak Expiratory Flow Rate				
Dermatology Patch: Nickel Sulfate				
Dermatology Patch: Cobalt Dichloride				

[†] p-value is based on an ANOVA for comparing the means between Area 3, and Areas 1, 2, 4, and 5; after adjusting for difference in the age and sex distribution of the two populations.

^{*} s.d. = standard deviation

Table 9.
Comparison of the Selected Measures of Chemicals Among Participants, by Sampling Areas, CHAP Comprehensive Health Questionnaire, Fall 2002

	Area 3	Areas 1, 2, 4, 5	Total for Port Colborne	p-value [†]
Chemical	Mean (s.d) [*]	Mean (s.d)	Mean (s.d)	
Nickel (Urine)				
Copper (Urine)				
Cobalt (Urine)				
Arsenic (Urine)				
Mercury (Urine)				
Lead (Blood)				

[†] p-value is based on an ANOVA for comparing the means between Area 3, and Areas 1, 2, 4, and 5; after adjusting for difference in the age and sex distribution of the two populations.

^{*} s.d. = standard deviation

Table 10.
Comparison of the Proportion of Tests Outside Normal Range for Selected Biological Measures,
by Sampling Areas,
CHAP Comprehensive Health Questionnaire, Fall 2002

	Area 3	Areas 1, 2, 4, 5	Total for Port Colborne	p-value [†]
Proportion Outside Normal Range				
Haemoglobin (normal range)				

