Appendix 10.3: Instruction to Subjects

Preliminary Content for General Instructions To Subjects

1 General Instructions Prior to Visit 1

All subjects are responsible for picking up their 24-hour urine specimen collection vessel before Visit 1, Day 1. Upon return to the central facility on Visit 1, Day 1, the subject is required to bring back the urine specimen collection vessel, having filled it over the previous 24-hour period.

Subjects also will be instructed before Visit 1, Day 1 to bring the name and contact information of their family physician. On the Adult Consent Form/Information Sheet and the Parent or Guardian Consent Form/Information Sheet, subjects are given the option to provide this information should they want their medical test results, or those of their children, forwarded to their family physician. Therefore, subjects should have their physician's name and telephone number on hand for Visit 1, Day 1.

2 Instructions for Urine Collection over 24-Hour Period

To ensure the most accurate reading of the urine specimen, special care must be taken in its collection. Please note the following:

- Be advised that there are potentially hazardous preservatives within the collection container.
- Discard the first morning specimen and record this time of voiding.
- Collect all subsequent voided urine for the remainder of the day and night.
- Collect the first morning specimen on day two at the same time as noted on day one.

3 Instructions for T.R.U.E. (Thin-layer Rapid Use Epicutaneous Test)

3.1 Instructions Prior to Visit 1, Specific to T.R.U.E.

Before you have the patch test performed (Visit1), you should:

- NOT consume seafood (i.e., shellfish)
- NOT apply topical corticosteroids (e.g. hydrocortisone) to the patch test area (your back) for one to two weeks before your test date (Visit 1);
- NOT take oral corticosteroids at a dose equivalent to or greater than 15 mg of Prednisone within one week of your test date (Visit 1);
- NOT take an injectable corticosteroid within one month of your test date (Visit 1);
- NOT take oral cyclosporin within one week of your test date (Visit1);
- NOT apply lotions, creams or ointments to the test area before the test (Visit 1);
- Minimize sun exposure to the test area before the test (Visit 1).

Note: Excessive back hair may have to be shaved before patch testing to allow for adhesion of the test strips.

At the time of your first visit (Visit 1, Day 1), you must NOT:

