Appendix 10.5: Metal Tests Information Table

Test Name	Methodology	Specimen Type	Specimen Required	Specimen Minimum Volume	Specimen Transport Temperature	Reference Values
Lead with Demographics	Inductively Coupled Plasma-Mass Spectrometry (ICP-MS)	Blood	
 ▪ Draw blood in a royal blue-top (EDTA) Monoject trace element blood collection tube – product 8881-307022 (Supply T183) and send 2.0 ml (pediatric [≤ 15 years]: 0.5 ml – Becton Dickinson MICROTAINER {Supply T174} of EDTA whole blood. 	0.5 mL	Refrig\Frozen OK\Ambient OK	
Pediatric (≤ 15 years)
 
 ▪ Normal: <10 ug/dL ▪ Toxic concentration: $>$ or $=20$ ug/dL 
Adults:
 
 ▪ Normal: <20 ug/dL ▪ Toxic concentration: $>$ or $=70$ ug/dL
Arsenic, Urine	Inductively Coupled Plasma-Mass Spectrometry (ICP-MS)	Urine	
 ▪ 10 mL from a 24-hour urine collection. No preservative. ▪ Collect in clean, plastic urine container(s) with no metal cap(s) or glued insert(s). ▪ Send specimen in a plastic, 13-mL urine tube or a clean, plastic aliquot container with no metal cap or glued insert. ▪ Refrigerate specimen within 4 hours of completion of 24-hour collection. Send specimen refrigerated. Note: Patient should not eat seafood for a 48-hour period prior to start of collection. 	1.0 mL	Refrig\Frozen OK\Ambient NO	
 ▪ Normal: <120 ug/specimen ▪ Toxic concentration: $>$ or $=5,000$ ug/specimen 
Note: The reference value is for a 24-hour collection.

[figure not shown]

Test Name	Methodology	Specimen Type	Specimen Required	Specimen Minimum Volume	Specimen Transport Temperature	Reference Values

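### Prosthesis and supplement sources of cobalt are not recorded as promised, and the participants' urine instructions do not match the laboratory's preservative and seafood requirements

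*Protocol*

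**What the plan says.** Section 3.4 (Study Limitations) discusses sources of metal other than the refinery. It states "Confounders include, diet and food in general", notes that shellfish can raise arsenic, and says that fractionated arsenic will separate the organic from the inorganic form. On cobalt it states "Cobalt could be elevated due to the presence of a prosthesis device". It then promises: "This will all be clearly addressed during the review of each participants data and in the analysis". The same paragraph goes on to list health supplements, including those with vitamin B12, which section 1.2.1.3 describes as a cobalt compound.

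Appendix 10.3 is the participants' instruction sheet. Its part on 24-hour urine collection warns: "Be advised that there are potentially hazardous preservatives within the collection container". That part does not mention seafood. The only seafood line is in the later part on the patch test: "NOT consume seafood (i.e., shellfish", with no period attached.

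Appendix 10.5 is the metals laboratory's table. For total arsenic it asks for "10 mL from a 24-hour urine collection. No preservative", and it likewise excludes preservative for fractionated arsenic, copper, mercury, nickel and cobalt. The total arsenic row adds: "Patient should not eat seafood for a 48-hour period prior to start of collection".

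Section 6.2.2.2 says both fractionated and non-fractionated arsenic will be evaluated. Mock Tables 9 and 12 (section 6.5.1) each have one urinary arsenic row. Section 6.4 places participants in tertiles of their measured exposure and compares the highest with the lowest by logistic regression.

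**The concern.** A confounder can be adjusted for only if it was recorded. If no one is asked about a prosthesis, a raised cobalt value from an implant cannot be told apart from one due to the environment, and no later analysis plan can recover the information.

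The specimen instructions raise a related problem. Participants follow the sheet they are given, not the laboratory's table. If the two disagree on what is in the container, or if the sheet omits the laboratory's dietary restriction, specimens may be collected under conditions the laboratory did not specify. That cannot be put right after collection.

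At stake are the tertile odds ratios based on urinary arsenic and cobalt, the comparison of metal levels between Area 3 and the other areas (Table 9), and the proportions outside the normal range (Table 12).

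**Working it through.** **1. Is the printed questionnaire complete?** Section 3.2 states 104 questions. Counting Appendix 10.1:

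- Background: 10 demographic + 2 residential + 2 occupational + 21 lifestyle/dietary + 1 educational + 3 other exposure = 39
- Health-related quality of life: 4
- Current medical health status: 50
- Mood: 11
- Total: 39 + 4 + 50 + 11 = 104

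This reproduces the stated figure, so an item not found there is absent from the plan and not lost in the text.

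**2. Named confounders against their data source.**

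| Confounder in section 3.4 | Where the data would come from |
|---|---|
| Shellfish (arsenic) | Fractionated arsenic assay; no question |
| Atopy (asthma) | Allergy, asthma and dermatitis/eczema items, in part |
| Jewellery piercing the skin (nickel sensitivity) | Background Q37 to Q39 |
| Prosthesis (cobalt) | None; could appear by chance in the open item on other long-term conditions (Q49) |
| Supplements, including B12 | Only the open item on any other medication (Q50v) |
| Diet in general | Drinking-water and garden items; nothing on food eaten |

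The prosthesis has neither a question nor an assay behind it.

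**3. Preservative.** Appendix 10.3 says preservatives are in the container. Appendix 10.5 says none for all six urine assays it lists: total arsenic, fractionated arsenic, copper, mercury, nickel and cobalt. Both cannot hold for the same 24-hour collection.

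**4. Seafood window.** The laboratory's period is 48 hours before the start of collection, and the collection lasts 24 hours. The window therefore opens 48 + 24 = 72 hours before the last void. That void is a first-morning specimen, so for a visit later in the day the window opens more than 72 hours before the visit. The participant sheet gives no period, narrows seafood to shellfish, and places the line under a different test.

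**5. Why the arsenic measure matters.** Appendix 10.5 treats total arsenic below 120 ug/specimen as normal, and inorganic arsenic of 25 ug/specimen or more as toxic. A specimen with total 100 and inorganic 30 is normal on the first (100 < 120) and toxic on the second (30 ≥ 25). A single arsenic row does not say which classification Table 12 reports.

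**6. Size.** The documents give no frequency of seafood intake, prostheses or supplement use, and no effect of a preservative on any assay, so the actual effect cannot be calculated. The following simulation shows only how such an error would act, and every input is an assumption: 5% prevalence in the lowest tertile, a true highest-versus-lowest odds ratio of 2.10, 333 people per tertile (1,000/3), and a random share of people whose log exposure is shifted upward.

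| Share shifted | Shift (SD) | Top tertile truly in it | Observed OR | Power |
|---|---|---|---|---|
| 0% | none | 100% | 2.10 | 68% |
| 10% | 1 | 90% | 1.97 | 60% |
| 40% | 2 | 54% | 1.52 | 28% |

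Dilution is the expected direction only when the shift is unrelated to the health outcome. If implants or supplement use go with age or illness, the bias could run either way.

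**The case against.** The strongest reply concerns arsenic. A reader might infer that seafood is left unhandled. It is not: section 3.4 names fractionation as the remedy, section 6.2.2.2 lists it as an outcome, and Appendix 10.5 gives it a method and its own limit. A laboratory measure can meet the promise without a question, and this stands. The seafood gap therefore falls mainly on total arsenic.

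It is also fair to say that the seafood text is an incomplete and misplaced instruction rather than a contradiction. Participants are told before Visit 1 not to eat it, and section 4.2.4.2.2 has the interviewer confirm compliance over the preceding days. But that check is general, comes after the urine has been handed in at sign-in, and describes no seafood field.

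On preservatives, a note to Appendix 10.5 says the laboratory's special instructions will be followed, section 5.4 requires metal-free containers, and Appendix 10.3 is headed as preliminary. These soften the point, but none says which statement is true, and section 4.2.3.2 relies on that sheet for the collection procedure.

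Which arsenic measure defines the tertiles could be left to a statistical analysis plan. The mock tables, however, are in the protocol and show no separate row for the fractionated result.

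A reader might also infer that every logistic model is affected. Section 6.4 uses questionnaire exposure as well as specimens, and models based on questionnaire exposure do not depend on the urine result.

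**Conclusion.** The point holds in a limited form. The prosthesis promise for cobalt has no data behind it, and supplements are captured only by chance. The preservative statements contradict each other for every urine metal. The laboratory's seafood window does not reach the participants' urine instructions. The plan's own arsenic remedy is not carried into Tables 9 and 12.

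The consequence is a risk that arsenic and cobalt exposure are misclassified in the specimen-based models and in the proportions outside the normal range. The documents do not show that misclassification occurs, and they do not support putting a figure on the share of the top tertile that seafood eaters or people with implants would fill. Seafood bears on arsenic, and prostheses and B12 supplements on cobalt. Only the preservative question could reach all the urine metals, and no effect of a preservative on any assay is documented.

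The matter should be settled before fieldwork, because neither unrecorded confounders nor specimens collected under the wrong instructions can be recovered afterwards.

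**What to change.** 1. Add three short items at Visit 1: any metal implant or prosthesis; vitamin or mineral supplements; and seafood eaten from 48 hours before the start of the urine collection until its end. Tie the seafood item to the collection rather than to the visit. Use the answers for adjustment or in a sensitivity analysis.
2. Reconcile Appendix 10.3 with Appendix 10.5 on preservative and on the seafood window before containers are issued, and put the agreed seafood wording in the urine-collection part of the sheet.
3. Name inorganic (fractionated) arsenic as the arsenic exposure for the tertiles and for Tables 9 and 12, and report total arsenic descriptively.

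The cost is about a minute of interview time, a revised instruction sheet and changed table labels. No new assay is needed, since fractionated arsenic is already planned.

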4.0 Methodology

4.1 Sampling Procedures

A sampling strategy that addresses the primary objectives of the health questionnaire, and satisfies the sample size estimated as a necessary requirement for meaningful comparisons to be made (section 7.0) is critical to the success of the study. A random sample of 1,000 individuals will be selected from an eligible population of Port Colborne residents. In order to obtain a representative sample of this community, it is necessary that the individuals who are included are selected from a comprehensive and fairly complete enumeration using an unbiased approach. Random selection is a preferred sampling method that can be used to avoid selection bias. However with any approach there will always be some bias. In this case, there will be an element of self-selection when subjects are given the choice to participate. In most cases, willingness to participate in a study is linked to the personality of the subject and an openness to participate in research. For this reason, when analyzing the results, it will be critical to assess whether non-response is systematically linked to the purpose or to the content of the study, or to some specific characteristic (e.g., socioeconomic status), thereby limiting the generalizeability of the study. This can be done by comparing demographics characteristics of the sample to the population of Port Colborne, using data from the Canadian census.

Further to randomization, a stratified sampling approach will be taken. In stratified sampling, the population is divided into strata, or groups that have certain characteristics

in common, and a sample is drawn from within each stratum. In this study, the strata will be defined as geographic areas categorized by approximation to level of exposure to the chemicals of concern. Stratified random sampling has several advantages over random sampling alone. First, by stratifying it can be ensured that each subgroup of the population is represented and that the carefully designed allocation of subjects can permit comparisons across strata. Second, when the population can be subdivided into groups that are more homogeneous than the population as a whole, more precise estimates of population parameters are obtained than when a random sample is taken of the whole population. This is because the variance computed for the entire sample is based on each within-stratum variance. Finally, strata can be constructed so that those that may have the largest number of individuals of interest (i.e., those with high exposures) can be sampled most heavily (Kelsey et al., 1996).

In order to perform comparisons among those individuals with potentially higher levels of exposure, an “oversampling” of residents in the Rodney Street area of Port Colborne must be done. Specifically, a proportionally higher number of people in this area will be included in the study relative to other areas of the city. The inclusion of a larger subsample in this area will allow for analysis of the results within this stratum and for comparisons to be made between this stratum and the rest of Port Colborne. Thus, even though the health questionnaire and the medical testing will not necessarily be administered to all residents of the Rodney Street area, the sample that emerges from that area will be large enough to be representative of the whole Rodney Street area in the

same way that the total sample (after weighting to adjust for oversampling) will be representative of the whole population of Port Colborne.

In addition to the weighting that adjusts for the oversampling in the Rodney Street area, it may be necessary to make adjustments to the sample if there are more people in one demographic category or other grouping than there should be, based on the real or true distribution of these groups in the population. Using available census data, combined with the observable demographic characteristics of the created sample, mathematically-derived weighting formulas will be considered to put the final, weighted sample in line with what it should be based on the characteristics of the population. Although many mathematical adjustments are rarely required to bring a sample into line with the real distribution characteristics of a population, most studies involving large samples do require a re-weighting to some degree.

4.1.1 Population

Port Colborne has a population of 18,450. From this population, a sample of 1,000 people who are at least 12 years of age will be randomly selected to participate in the health questionnaire and the medical testing. This sample will be chosen from a listing of all households based on phone numbers.

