3.0 Study Design

3.1 Overview

To accomplish the objectives outlined above, data will be gathered from a stratified random sample of 1,000 Port Colborne residents aged 12 years of age and older. Each participant will be asked to complete a questionnaire and undergo medical testing.

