6.1.1 Power calculations for the health questionnaire

Power was calculated based on the primary objective of the study which is to characterize the current health of residents in Port Colborne using a comprehensive health assessment questionnaire and medical testing. As mentioned previously, a stratified sampling strategy will be applied to recruit individuals from five geographical areas. The sample size of the Health questionnaire and medical tests was calculated by determining the number of individuals needed to measure the prevalence of selected health conditions with sufficient precision both within the Rodney Street Area, and the remainder of Port Colborne. Specifically, the sample size of 1,000 was selected to ensure that a 5% prevalence of asthma could be measured within an accuracy of 2% 16 times out of 20, and that the prevalence of nickel sensitivity estimated at 9.5% among women could be measured within 7% and 13% 16 times out of 20 (see Table 1 below).

Table 1: Sample Size Needed to Compare Disease Prevalence Rates (Proportions)

Health Condition	Anticipated Prevalence	Prevalence Range Permitted**	Subjects needed in Area 3	Subjects needed in remainder of Port Colborne	Minimally detectable Odds Ratio*
Asthma	5%	4-6%	418	777	2.0
Asthma	5%	3-7%	160	193	3.2
Asthma	5%	4.5%-5.5%	699	2662	1.7
Cancer	0.5%	0.4-0.6%	811	5630	3.4
Nickel Sensitivity (females)	9.5%	8%-11%	370	607	1.8
Nickel Sensitivity (females)	9.5%	7%-13%	181	223	2.4

* Comparison of prevalence of disease between Area 3 and the rest of Port Colborne

**with Power of 80% and an alpha error of 5%

Assuming that there is a response rate of 65%, and that 50% of residents in the region are female, there will be 234 female participants in the Rodney Street area and a remaining 251 female subjects in the rest of Port Colborne. This will enable nickel sensitivity to be measured with sufficient precision as outlined in the table above. Moreover, when supplemented with data obtained from males, there will be sufficient precision to measure the prevalence of asthma within an accuracy of 2% in both sexes (see Table 1). It is important to note that due to the rarity of cancer, the health questionnaire is unable to measure the prevalence of cancer in Port Colborne with sufficient precision. The evaluation of this health outcome will be addressed in a subsequent research protocol.

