The estimated number of dwellings and individuals that make up the target population are listed in Table 1. This list is considered approximate as it is based on Canadian census data obtained in 1996.

Table 2: Estimated Number of Households and Individuals 12 years of Age and Older* within Each Sampling Region for the health questionnaire.

Region (EA's)	Number of private dwellings	Estimated population 12 years of age and older
1- West of the Welland Canal, south of Clarence and Augustine Road (151-156)	1,945	4,055
2- West of the Welland Canal, north of Clarence (116-120)	2,260	4,798
3- East of the Canal, south of Durham (includes Durham) and is bounded by Davis and Lake (110)	365	719
4 - East of the Canal, north of Durham (excludes Durham) and is bounded by Snider Road (106,108)	775	2,346
5- Other areas of Port Colborne (101-105,107,109,112-113)	2,030	4,437
Total	7,375	16,355

* assumes that 85% of the Port Colborne community is 12 years of age and older (based on 1996 Census data from Statistics Canada).

It is very important to note that while there are sufficient numbers to measure the prevalence of the selected health conditions with the desired precision, there is limited power to make comparisons between rates in the Rodney Street area to the remainder of Port Colborne. Specifically, with 500 subjects recruited in both the Rodney Street area and other parts of Port Colborne, the study has the power to detect an odds ratio of 2.1 for the comparison of asthma rates between the two regions with a power of 80% and a type I error rate of 5%. The odds ratio of 2.1 corresponds to a greater than two-fold increased prevalence rate in area 3 relative to the rest of Port Colborne. Similarly, for a comparison of nickel sensitivity rates in females between the two regions, there is power to detect an odds ratio of 2.2.

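### The 1,000 is the number selected in sections 4.1 and 4.1.1 but the number of participants in 3.1 and 6.1.1, and the 234 + 251 women in 6.1.1 fit neither reading

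*Protocol*

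**What the plan says.** Two groups of statements give the 1,000 different meanings.

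**Selected, before anyone agrees.** Section 4.1: "A random sample of 1,000 individuals will be selected from an eligible population of Port Colborne residents". Section 4.1.1: "a sample of 1,000 people who are at least 12 years of age will be randomly selected to participate". The synopsis uses the same language. Section 4.1 adds that "there will be an element of self-selection when subjects are given the choice to participate", and section 4.2.4.1 places contact and the request to participate after random selection.

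**Participating.** Section 3.1: "data will be gathered from a stratified random sample of 1,000 Port Colborne residents aged 12 years of age and older". Section 6.1.1 bases its detectable odds ratios on a study "with 500 subjects recruited in both the Rodney Street area and other parts of Port Colborne".

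Section 6.1.1 also brings in non-response, at a rate of 65%, and takes half of residents to be female. From those two assumptions it concludes that "there will be 234 female participants in the Rodney Street area and a remaining 251 female subjects in the rest of Port Colborne". Table 2 in that section gives Area 3 as 365 dwellings and 719 people aged 12 or over.

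On replacement, section 4.1.1.2 says that further subjects will be sampled to make up for drop-outs. It does not mention people who refuse at first contact. Section 4.1.3 sorts the telephone listings in each area by a random number, but gives neither a number to approach nor a stopping rule.

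**The concern.** A sample size has to say whether it counts people approached or people who take part. At a 65% response the two differ by about a third. Here the same 1,000 is used for both, and the response rate appears only in the count of women. Field staff working from 4.1 and 4.1.1 could draw 1,000 names and stop, while the stated odds ratios assume 1,000 participants. The two readings lead to different studies, and the difference cannot be recovered once the two-month collection period has closed.

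**Working it through.** **Inputs.** 65% response, 50% female, 234 and 251 women, 500 + 500 recruited, stated odds ratios 2.1 (asthma) and 2.2 (nickel, women) at 80% power and 5% type I error, and Table 1 needs: all from 6.1.1. Area 3 population 719: Table 2. Prevalences 5% (asthma) and 9.5% (nickel, women): Table 1. Two-sided testing is assumed, since it is not stated.

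**1. Where the 234 and 251 come from**
- 719 × 0.65 × 0.50 = 233.7, so 234 is everyone in Area 3 approached.
- 251 / (0.65 × 0.50) = 772 people approached in the rest.
- 719 + 772 = 1,491 approached. (234 + 251) / 0.50 = 970 participants.
- If 1,000 were approached: 1,000 × 0.65 × 0.50 = 325 women.
- If 1,000 took part: 1,000 × 0.50 = 500 women.
- The stated total is 485, which matches neither.

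**2. Reproducing the stated odds ratios**

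Method: two-proportion normal approximation with pooled variance under the null, solved for the odds ratio giving 80% power. Area 3 prevalence is p₁ = OR·p₀ / (1 − p₀ + OR·p₀), where p₀ is the prevalence in the rest. Power = Φ[(|p₁ − p₀| − c − 1.96·SE₀)/SE₁], with c = 0, or c = ½(1/n₁ + 1/n₂) for the continuity correction.

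| Comparison | n (Area 3 / rest) | Detectable OR, without / with correction | Stated |
|---|---|---|---|
| Asthma | 500 / 500 | 2.02 / 2.07 | 2.1 |
| Nickel, women | 234 / 251 | 2.13 / 2.20 | 2.2 |

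The stated values are recovered, so they describe a study of about 1,000 participants.

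**3. If 1,000 people are approached** (650 participants, 325 women)

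| Split | Comparison | n (Area 3 / rest) | Detectable OR, without / with correction | Power at stated OR |
|---|---|---|---|---|
| Even (assumed) | Asthma | 325 / 325 | 2.33 / 2.42 | 67% / 62% |
| Even (assumed) | Nickel, women | 162.5 / 162.5 | 2.47 / 2.58 | 67% / 61% |
| All 719 of Area 3 approached | Asthma | 467 / 183 | 2.59 / 2.70 | 53% / 46% |
| All 719 of Area 3 approached | Nickel, women | 234 / 91 | 2.75 / 2.90 | 53% / 46% |

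In the second split, 1,000 − 719 = 281 are left to approach in the rest; 281 × 0.65 = 183 participants, of whom about 91 are women.

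**4. Precision**

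The half-width at 80% confidence (16 times out of 20) is 1.2816·√[p(1 − p)/n·(1 − n/N)]. Most Table 1 counts reproduce with N of about 900 for Area 3 and 18,000 for the rest. These values of N are inferred, not stated. The nickel row for 7-13% (181 and 223 women) reproduces at a half-width of 2.5 points.
- Nickel, even split: 2.7 and 2.9 points, so about 6.8-12.2% and 6.6-12.4%. The Table 1 counts are missed, but the 7% limit is missed by only 0.2-0.4 points.
- Nickel, 234/91 split: 2.1 points in Area 3 and 3.9 points in the rest, with 91 women against 223 needed.
- Asthma, even split: 1.2 and 1.5 points, within the 2-point target.

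**5. If 1,000 is the participant target**

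1,000 / 0.65 = 1,538 approached. Area 3 can give at most 719 × 0.65 = 467, since 500 / 0.65 = 769 exceeds 719. A 467/533 split gives 234/266 women. Detectable odds ratios are then 2.02 / 2.07 for asthma and 2.11 / 2.17 for nickel, so the stated 2.1 and 2.2 still hold.

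**The case against.** The strongest reply is that 1,000 was always meant as participants. Section 3.1 says data come from 1,000 residents, section 4.1 opens by tying the sampling strategy to the required sample size, and 6.1.1 speaks of subjects recruited and has already applied the 65% to its count of women. The first mock table counts households selected and refusals separately, so the authors plainly expected to approach more households than they would enrol. Nothing in 4.1.3 forbids continuing down the random list, and 4.1.1.2 concerns withdrawal and is simply silent on refusals.

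Most of this stands. A reader might infer that the study will be a third too small, or that only drop-outs may be replaced. The document supports neither: the loss follows only if 1,000 is taken as the number approached, and silence on refusals does not exclude replacing them. A reader might also infer that every precision target fails at 650. At an even split the asthma target is met and the nickel target is missed narrowly.

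The reply does not remove the conflict. Sections 4.1 and 4.2.4.1 put selection before the choice to take part, the 485 women do not fit 1,000 participants either, and the number to approach is never given. The 15-woman gap in the rest (251 against 266) is small and conservative, and does not change the stated odds ratio of 2.2.

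**Conclusion.** The inconsistency is established; the shortfall is conditional. The protocol gives 1,000 two meanings, and its counts of women rest on about 1,490 people approached, which it does not state. If 4.1 and 4.1.1 are followed literally, about 650 people take part and neither stated odds ratio keeps 80% power: 61-67% at an even split, 46-53% if all of Area 3 is approached. Nickel precision clearly fails only in the second case, in the rest of the city.

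These figures assume two-sided 5% tests, the protocol's own 65% and 50%, and the splits shown. The even split is an assumption; the other is the one the 234 implies. Whether Area 3 can in practice yield 467 participants, with one resident chosen per household (4.1.3) and 365 dwellings, is a separate question that this point does not settle.

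**What to change.** If 1,000 is the participant target:
- Say so in the synopsis, 4.1 and 4.1.1, matching 3.1 and 6.1.1.
- State the number to approach in each area at 65% response, about 1,540 in total.
- State that selection continues down the random list after refusals until the area target is met.
- Recompute the 234/251 women and the 500 recruited per side from that allocation. On Table 2's figures Area 3 cannot exceed about 467. A 467/533 split (234/266 women; 719 and about 820 approached) leaves the odds ratios of 2.1 and 2.2 unchanged.

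If 1,000 is the number approached, restate the detectable odds ratios and the nickel precision for 650 participants and give the split used.

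On the first route the cost is wording and a few recomputed counts. The field workload is what 6.1.1 already implies, apart from the Area 3 count falling from 500 to about 467 and about 50 more people to approach than the roughly 1,490 behind the 485 women. On the second route the cost is restated figures and acceptance of lower power. Either is cheap before fieldwork starts.
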